4. STATISTICAL ANALYSIS

Descriptive summary statistics will be presented for the study sample, and will include sociodemographic information, obstetrical histories and delivery details. Data will be summarized using frequency distributions for categorical variables, means and medians for continuous variables. A sex and gender-based analysis plus (GBA+) framework will be applied throughout to investigate both sex and gendered related aspects of vaccination among pregnant and their infants including, social and geographic position, race, age, sexuality, sex and gender.

Relative antibody levels will be reported on all positive tests as geometric mean (GM) and their 2-sided 95% confidence intervals (CIs). The maternal response to vaccination will be determined by anti-SARS-CoV-2 antibody levels in maternal serum. Antibody GM with 95% CIs will be compared across time points and between study groups for each sample type. The contribution of IgG subclasses to the total SARS-CoV-2 antibody response will also be reported. Extent and duration of antibody transfer to breastmilk/chestmilk will be evaluated. Infant antibody titres will also be examined to investigate the extent and duration of passive immunity conferred through antibody transfer via the placenta or breastmilk/chestmilk, if any.

Cytokine data will be correlated to detected antibody isotype titres to identify integrated, multi-factorial maternal and newborn immune response signatures to COVID-19 vaccination.

We will account for timing of maternal vaccination in pregnancy/postpartum, vaccine product, number of vaccine doses, COVID-19 infection history, and receipt of other vaccines (mother/child) within the study follow-up period in all analyses.

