3.4. Study Outcomes

3.4.1. Primary Outcomes

[figure not shown]
The primary outcome of interest will be immunogenicity of COVID-19 vaccines. We will measure:

- Seroconversion rates in vaccinated mothers
- SARS-CoV-2 antibody titres and their persistence in mothers after vaccination in pregnancy
- Transfer of antibodies to breastmilk/chestmilk
- Transfer and persistence of SARS-CoV-2 antibodies to the neonate/infant over the study period.
- Other immune response markers in mothers and infants
- Comparing infection-acquired and vaccine-acquired immunity against COVID-19 in mothers and newborns (Objective 3: COPE Substudy)
- Comparing immune responses to COVID-19 vaccination in pregnant and non-pregnant women/individuals (Objective 4: SSO Substudy)

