3.7.3. Sample Analysis

Data derived from sample analysis will be linkable to the data file generated from primary and secondary data collection.

Antibody Response to Vaccination

[figure not shown]
Blood and breastmilk/chestmilk samples will be evaluated for antibodies to SARS CoV-2 and neutralizing antibodies to assess maternal and newborn immune responses to maternal vaccination in pregnancy. All samples will be analyzed using a high-throughput enzyme-linked immunosorbent assay based on previously published methods.^{12,13} The assay probes for IgA, IgM and IgG anti-SARS-CoV-2 antibodies and also maintains sensitivity in the detection of antibodies raised against variants of concern: P1, B.1.1.7 and B.1.351. The serological assay detects antibodies against the nucleoprotein (N), the receptor binding domain (RBD) and the full trimeric spike (S). Test sensitivity is 100% at 10 days post-symptoms and specificity is 99.2% as tested against pre-pandemic samples (manuscript in preparation). Such a strategy can distinguish infection-acquired immunity (against N+S+RBD) vs vaccine-induced immunity (S+RBD only). We will also run Neutralization assays (snELISA) on the full spike protein, based on previously published methods.¹⁴ A positive cut-off will be established, equal to the mean of the optical density (OD) values of the negative control samples on the respective plate plus 2x the standard deviation of the OD value distribution from pre-COVID-19 plasma/serum. Background-corrected OD values will be divided by the cut-off to generate signal-to-cutoff (S/CO) ratios. Samples with S/CO values greater than 1.0 will be considered positive. Relative antibody levels measured against a standard curve will also be reported.

Biomarker evaluation

To add understanding to the immunological microenvironment driving the quality and quantity of maternal and newborn antibody responses to maternal COVID-19 vaccination, serum samples will be analyzed for relevant biomarker expression (e.g., serum cytokines). Multiplex immunobead-based assays (BioRad) will be used to quantify serum cytokines.

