3.7.4. Sample Retention

Placental biopsies and unused blood and breastmilk/chestmilk samples will be stored at the SCC for future research (e.g., placenta immunohistochemistry, metabolomic analyses). Banked samples, when paired with the detailed PLAN-V dataset will be an important resource for future research.

Objective 3 - COPE Sub-study

Comparing immune responses to COVID-19 vaccination and natural COVID-19 disease among pregnant women/individuals and their infants exposed in utero

Study design: A cross sectional analysis of maternal and infant samples at the time of delivery.

Study Population: We will use samples collected at the time of delivery from mother-infant dyads who were enrolled in the current PLAN-V study and the PI's CIHR-funded COPE Network study (CTO ID 2168).³

[figure not shown]
- **PLAN-V study participants:** Mother-infant dyads in which mothers received at least one dose of the COVID-19 vaccine in pregnancy (any type). Eligible dyads will be those where mothers had no COVID-19 infection history and from whom maternal blood and infant cord blood samples were collected at delivery (i.e., vaccinated mother-infant dyads from the pregnancy group).
- **COPE Network study participants:** The COPE Network Study is an ongoing pregnancy and birth cohort study of mothers with documented COVID-19 infection during pregnancy.³ COPE Network study participants contributed both maternal blood and infant cord blood samples at delivery. Samples from more than 100 dyads have been collected to date.

Exposures: The exposure of interest is maternal COVID-19 vaccination (PLAN-V Study) or infection (COPE Network Study) in pregnancy.

Outcome Measures: **The primary outcomes are:** seroconversion rates and antibody titres in pregnant women/individuals after COVID-19 vaccination and COVID-19 disease in pregnancy; trans-placental transfer of antibodies to neonates with *in utero* exposure to COVID-19 vaccination compared to COVID-19 disease; and differences in antibody transfer to breast/chest milk where samples are available. (Breastmilk/chestmilk samples are available from 50% of COPE Network participants). **Secondary outcomes** will be the nature and frequency of pregnancy and newborn outcomes at delivery.

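### Antibody geometric means are limited to positive tests yet compared over time and between groups, which understates decline and distorts group contrasts wherever many samples are negative

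*Protocol*

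**What the plan says.** Section 4 (Statistical Analysis) fixes which results enter the mean: "Relative antibody levels will be reported on all positive tests as geometric mean (GM) and their 2-sided 95% confidence intervals (CIs"). Two sentences later it says what the mean is used for: "Antibody GM with 95% CIs will be compared across time points and between study groups for each sample type".

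Section 3.7.3 defines a positive result: "Samples with S/CO values greater than 1.0 will be considered positive". It adds: "Relative antibody levels measured against a standard curve will also be reported". These relative levels are the quantity that Section 4 then restricts to positive tests.

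The GMs serve outcomes listed as primary in Section 3.4.1:

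- for mothers, "SARS-CoV-2 antibody titres and their persistence in mothers after vaccination in pregnancy"
- for milk, whether antibody passes into it
- for infants, "Transfer and persistence of SARS-CoV-2 antibodies to the neonate/infant over the study period"
- the comparisons with the COPE and Stop the Spread Ottawa (SSO) cohorts.

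The COPE sub-study (Objective 3) is "A cross sectional analysis of maternal and infant samples at the time of delivery". In the SSO sub-study (Objective 4), antibody titre in pregnant versus non-pregnant participants is the primary immunological measure.

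**The concern.** Being positive is part of the outcome. A participant whose level falls below the cut-off leaves the mean at that visit, and a non-responder never enters it. The set of samples averaged therefore changes with time and differs between groups, and a positives-only GM can never fall to the cut-off. Persistence becomes persistence among those who persisted.

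Three consequences follow:

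- Decline is understated if the spread stays stable.
- Group contrasts shrink when spreads are similar and the lower group has more negatives.
- When spreads differ, a contrast can appear although the true GMs are equal.

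The protocol makes negatives foreseeable. Sampling runs from before the first dose to 180 days after the last. Both sub-studies accept participants with a single dose. Section 4 itself allows that infants may receive no antibody. COPE is cross-sectional, so there the issue is the group contrast and not waning.

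**Working it through.** **The plan's own figures.** The Section 5 power statement (95% vs 80% seroconversion, 150 participants, 93% to 95% power) is sound and not at issue. A pooled z-test against 100 COPE dyads gives 94.7%, and a continuity-corrected test against 126 SSO participants gives 95.2%. The detectable GM ratio of 1.19 cannot be reproduced, because neither an SD nor a power is given. It can only be inverted:

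ln SD = ln(1.19) / [(1.96 + z_power) × √(1/150 + 1/n₂)]

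With n₂ from 100 to 150 and power from 95% down to 80%, this gives about 0.37 to 0.54.

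**Model (assumption).** Levels are lognormal, with mean μ and SD s on the ln scale, and the cut-off c corresponds to a fixed level. With a = (ln c − μ)/s:

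- share positive = 1 − Φ(a)
- positives-only GM = exp[μ + s·φ(a)/(1 − Φ(a))].

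**Decline.** GMs are in multiples of the cut-off.

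| ln SD | Positives-only GM at true 8 | at true 2 | at true 0.5 (share positive) | True 4-fold fall reads | True 16-fold fall reads |
|---|---|---|---|---|---|
| 0.7 | 8.03 | 2.45 | 1.45 (16%) | 3.27 | 5.55 |
| 1.0 | 8.38 | 3.03 | 1.81 (24%) | 2.77 | 4.64 |
| 1.3 | 9.32 | 3.79 | 2.27 (30%) | 2.46 | 4.10 |

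For example, at SD 1.0: 8.38/1.81 = 4.6 in place of 16.

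At the smaller SDs implied by the 1.19 ratio (0.37 to 0.54), the 4-fold fall reads 3.9 to 3.6 and the 16-fold fall reads 6.9 to 6.2.

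**Group contrast.** Section 5's planning rates, 95% and 80%, are used here as percent positive, so GM/c = exp(z_p·s), with equal spread in both groups.

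| log10 SD | True GM ratio | Positives-only ratio |
|---|---|---|
| 0.3 | 1.74 | 3.36/2.28 = 1.47 |
| 0.4 | 2.10 | 5.03/3.00 = 1.68 |
| 0.5 | 2.52 | 7.53/3.94 = 1.91 |
| 0.6 | 3.03 | 11.27/5.19 = 2.17 |

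At ln SD 0.37 to 0.54, true ratios of 1.35 to 1.54 read 1.23 to 1.35.

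**False contrast.** Both true GMs are 4 times the cut-off, with log10 SD 0.3 in one group and 0.6 in the other (98% and 84% positive). The ratio reads 4.15/5.94 = 0.70 in place of 1. At 16 times the cut-off it reads 0.93.

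**Where it does not matter.** At ln SD 1.0, a true 4-fold fall from 32 to 8 times the cut-off reads 3.8, and a true 2-fold contrast (16 vs 8) reads 1.9.

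**Interval coverage.** This used 4,000 simulations with 150 tested and a t-interval on ln positive values, at ln SD 0.7 to 1.3. The nominal 95% CI covers the all-sample GM about 94% of the time at 99% positive, about 70% at 95% positive, and essentially never (0.1% or less) at 80% positive.

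**The case against.** **The reading is an inference.** The restriction stands in a sentence about reporting. The comparison sentence does not repeat it, and a sentence on maternal response with no positivity limit lies between. This stands as a wording ambiguity. But the positives-only GM is the only antibody GM the protocol defines, so carrying it over is the natural reading.

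**Positivity is not ignored.** Samples are classed positive or negative, and seroconversion is reported. Proportion positive plus level among positives is a recognised two-part summary. However, the protocol does not promise percent positive beside each GM. Seroconversion in Section 3.4.1 is a maternal rate, and none of this corrects a comparison of the GMs themselves.

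**Handling of negatives belongs in an SAP.** The censoring model and any substitution value do. The restriction to positive tests does not: the protocol states it, and an SAP that followed it would carry the problem forward.

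**The examples favour large effects.** In part this is fair:

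- At the implied SDs of 0.37 to 0.54 the bias is smaller, though still in the same direction. Those SDs also rest on an assumed power.
- The false-contrast example doubles the spread. At log10 SD 0.3 vs 0.4 the ratio reads 0.91 at 4 times the cut-off and 1.00 at 16 times.
- The coverage figures concern a single GM. In a ratio, the bias cancels if percent positive and spread are equal.
- No document gives negative rates for milk, late infant or one-dose samples.

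**Conclusion.** The concern holds. Followed as written, Section 4 selects on the outcome for primary outcomes on persistence, transfer and group comparison. The effect on decline is understatement: the positives-only GM still falls, but by too little.

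The size depends on the share negative and on the spread, and the protocol gives neither. Under lognormal levels it ranges from negligible when nearly all samples are positive to a true 16-fold fall reading as 4- to 7-fold across ln SDs of 0.37 to 1.3. Group ratios at 95% vs 80% positive lose a noticeable part of their size at every SD tried. The direction for decline assumes a stable spread, and for group contrasts similar spreads. With unequal spreads the error can go either way.

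The powered seroconversion outcome is not affected. This should be fixed before analysis.

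**What to change.** In Section 4, base the GMs and their CIs on all tested samples in place of positive tests only. Then:

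- Pre-specify one rule for values below the cut-off or limit of quantification. A left-censored (Tobit-type) model is the better primary rule, with a fixed value below the limit as sensitivity analysis.
- Report percent positive beside each GM, by visit, group and sample type.
- Keep any positives-only GM as a labelled descriptive, and do not compare it across time or groups.

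Substituting half the cut-off already brings the 16-fold example to 13.5, 11.6 and 10.1 at ln SD 0.7, 1.0 and 1.3. That example is favourable, because the late true GM equals the substituted value. Substitution has its own floor: a true 80-fold fall from 8 to 0.1 times the cut-off reads only 15 to 16. This is why the censored model is preferred.

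The cost is wording and slightly more analysis, with no new samples. The protocol does not say whether negative samples receive a quantified level and gives no limit of quantification, so the laboratory must confirm both. A censored or fixed-value rule works either way. Reported GMs will look lower.

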1.2. Our Approach

We will build on existing resources and expertise available through the COVID-19 Ontario Pregnancy Event (COPE) Network - a collaboration of 13 obstetrical hospitals in 6 of Ontario’s largest cities - **to establish a prospective, longitudinal cohort study of pregnant women/individuals and their infants.** COPE Network sites collectively handle ~75% of in-hospital Ontario births. To-date, of the current COPE Network sites, 10 have been designated to run COVID-19 vaccine clinics and the other 3 are within proximity to a designated clinic.

We will launch an in-depth investigation of the immunogenicity of COVID-19 vaccines in pregnant women/individuals, and the role of maternal vaccination for the protection of their newborns. The study will include extensive Ontario-wide maternal and newborn bio-sampling in the prenatal, delivery and postpartum periods to address critical questions including: **(1) What is the immunogenicity of COVID-19 vaccines in this population, (2) What is the fetal/newborn immune response to maternal vaccination (3) Does timing of maternal vaccination in pregnancy affect fetal/newborn antibody transfer? (4) How durable are maternal and newborn immune responses? and (5) How do newborn immune responses differ between natural maternal COVID-19 infection in pregnancy versus maternal vaccination in pregnancy?** Our design will enable us to compile detailed longitudinal maternal-newborn clinical and immune response profiles beyond what can be accomplished from larger surveillance projects.

The framework for collaboration, participant recruitment and sample collection exist through the COPE Network infrastructure and we can rapidly operationalize this study. Since May 2020, the COPE Network has been collecting maternal and infant samples to generate complete infection and antibody profiles [CIHR-funded VR4-172760].³ To date, more than 150 SARS-CoV-2 infected participants have delivered at a COPE site, or are enrolled and pending delivery. The PLAN-V study is the natural progression of this work and will leverage existing study infrastructure to address key questions about immunogenicity of COVID-19 vaccinations in the pregnant population and the fetal/newborn immune response.

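### Placental antibody transfer has no defined metric, and the titre comparisons in Section 4 cannot separate it from the mother's antibody level at delivery

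*Protocol*

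**What the plan says.** Transfer to the newborn appears in three places in the protocol.

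- Section 1.2 lists as a study question: "Does timing of maternal vaccination in pregnancy affect fetal/newborn antibody transfer".
- Section 3.4.1 lists as a primary outcome: "Transfer and persistence of SARS-CoV-2 antibodies to the neonate/infant over the study period".
- The Objective 3 (COPE) sub-study names "trans-placental transfer of antibodies to neonates" as a primary outcome, compared between vaccination and disease in pregnancy. Its design is "A cross sectional analysis of maternal and infant samples at the time of delivery", and PLAN-V dyads qualify only if they are those "from whom maternal blood and infant cord blood samples were collected at delivery".

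None of these defines a measure of transfer. Section 4 states the analysis: "Antibody GM with 95% CIs will be compared across time points and between study groups for each sample type". On the infant it says: "Infant antibody titres will also be examined to investigate the extent and duration of passive immunity conferred through antibody transfer via the placenta", and the sentence goes on to include milk. Levels are reported on positive tests only. The analyses are to account for timing of vaccination, product, number of doses, infection history and other vaccines. Maternal antibody level at delivery is not in that list, and no within-dyad ratio appears anywhere in the protocol.

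Table 2 schedules maternal blood and cord blood at delivery.

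**The concern.** The cord titre is the maternal titre at delivery multiplied by the cord-to-maternal ratio. A contrast of cord titres between groups is therefore the product of two contrasts: one in maternal level and one in transfer.

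For the timing question the first is unlikely to be null. Gestational age at dose and time from dose to delivery add up to gestational age at birth, so a woman vaccinated early has had longer for her titre to fall. Adjusting for timing does not help, because timing is the exposure under study.

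In Objective 3 the size of the maternal response, and the time since infection or dose, can both differ between the cohorts, and both enter a cord-level contrast.

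At stake is a conclusion on when in pregnancy vaccination gives better placental transfer. Section 8 says that a national specialist society will review the findings for practice recommendations.

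**Working it through.** **The plan's own figures.** The protocol gives no figure for transfer. Its stated power (93% to 95% for seroconversion of 95% vs 80%, α = 0.05) concerns a different outcome and is not in question. A two-sided two-proportion test with continuity correction gives 92.3% for 150 vs 100 (the COPE count, given as more than 100) and 95.2% for 150 vs 126 (SSO), close to the stated range.

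**Step 1: waning alone.** Take two women with identical transfer, last dosed at 16 and 32 weeks and both delivering at 40 weeks. Section 3.2 admits vaccination at any stage of pregnancy, so both could enrol. The difference in time since dose is (32 − 16) × 7 = 112 days. With maternal half-life h in days (an assumption), the late-to-early fold difference in cord titre is 2^(112/h).

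| Assumed half-life | Exponent 112/h | Fold difference in cord titre |
|---|---|---|
| 90 days | 1.24 | 2.4 |
| 60 days | 1.87 | 3.6 |
| 30 days | 3.73 | 13 |

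The true difference in transfer is 1.0-fold in every row.

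**Step 2: level contrast against paired ratio.** A simulation on the natural-log scale set cord = maternal × transfer. All inputs are assumptions: half-lives of 45, 60, 90 and 120 days crossed with early-to-late gaps of 60, 90 and 120 days (12 scenarios), 75 dyads per group, ln-SD 0.8 for maternal level and 0.35 for transfer, two-sample t-tests, 2,000 runs each.

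| Truth | Early/late ratio from cord level | Level test rejects | Early/late ratio from paired cord/maternal | Paired test rejects |
|---|---|---|---|---|
| Equal transfer | 0.16 to 0.71 | 68% to 100% | 1.00 | 4% to 6% |
| Transfer 1.3 early vs 0.8 late (1.3/0.8 = 1.63) | 0.26 to 1.15 | 5% to 100% | 1.62 to 1.63 | about 100% |

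In the second row the cord-level ratio was below 1, the wrong direction for transfer, in 10 of the 12 scenarios. The paired ratio recovers the true value because maternal level cancels.

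**Step 3: is the pairing available?** Yes. Table 2 has both samples at delivery, and Objective 3 requires both from PLAN-V dyads and reports both for COPE participants. Objective 3 uses serum for mother and cord. In the main study, Section 3.7.1 lets the mother choose a dried blood spot, an option Table 2 does not attach to cord blood, so some pairs may differ in matrix.

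**The case against.** The strongest reply is that the protocol is silent on the metric and has not chosen a wrong one. A derived endpoint is often left to the statistical analysis plan, which is not shown and could define a ratio. The sentence on infant titres concerns passive immunity, for which infant titre is the right measure, and it may describe postnatal samples only, since Table 2 lists baby blood and cord blood separately. Comparing means by sample type may just describe presentation. Objective 3 takes the dyad as its unit and lists maternal titres and transfer as separate outcomes. Finally, the antibody that reaches the newborn is a legitimate target in itself, and for that target waning is part of the timing effect.

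Much of this stands. A reader might infer that the protocol rejected a paired ratio in favour of levels, that the timing question will be answered by maternal waning, or that Objective 3 will read any maternal difference as a transfer difference. The documents support none of these. They leave transfer undefined, a level contrast carries transfer as well as maternal level, and nothing says that one Objective 3 outcome will be read as the other.

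What the reply does not remove is that the only comparison Section 4 sets out for antibody levels is by sample type. An analysis plan that follows it would have no way to separate transfer from maternal level, and transfer is named as a question and an outcome in its own right.

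**Conclusion.** The point holds in a limited form: the transfer metric is undefined, and the stated level comparisons mix maternal level at delivery with placental transfer. This affects the timing question in Section 1.2 and the transfer outcome of Objective 3. Seroconversion, its power, and infant titre as a measure of passive immunity are unaffected.

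The mixing could be large, at 2.4- to 13-fold for a 112-day timing gap, and under the simulated inputs it could reverse the direction of a real transfer difference. These sizes are illustrative. They rest on assumed half-lives, gaps and standard deviations and on simple exponential decay, none of which the protocol gives. For vaccine versus infection no size can be stated, because the relative maternal responses are not given either.

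**What to change.** In Section 4 and in Objective 3:

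- Define transplacental transfer as the within-dyad log cord-to-maternal IgG ratio at delivery, reported as a geometric mean ratio with 95% CI.
- Use it as the outcome for the timing question and for the vaccine-versus-infection transfer contrast, with gestational age at birth as a covariate.
- Include every dyad whose mother has measurable IgG. Handle cord-negative samples by a stated rule, for example as left-censored at the assay limit, so that the positive-tests-only convention does not drop them.
- Restrict to dyads with maternal and cord samples in the same matrix, or analyse serum and dried-spot pairs separately.
- Interpret the timing result as the combined effect of gestational age at dose and dose-to-delivery interval. At a fixed gestational age at birth the two cannot be separated, and the ratio does not change that.
- Keep cord and infant titre as a separate outcome, labelled infant antibody level.

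The cost is wording and some lost dyads: those lacking one of the two samples, or with mismatched matrices, do not contribute to the ratio. No new visit or sample is needed.
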